## ***Clinical Trial Experience/Recruitment and Retention***

Our group has conducted several clinical trials and interventional studies utilizing CPAP involving collaboration with sleep medicine and cardiologists/electrophysiologists for which we have either met or exceeded recruitment goals and have had expected retention (drop out range: 10-20%). (*NIH/NHLBI HL079114: Oxidative Stress in Sleep Apnea and Cardiac Disease, NHLBI 1RC2HL101417: Phase II Trial of Sleep Apnea Treatment to Reduce Cardiovascular Morbidity, NHLBI R01 HL 109493: Elucidation of the Risk of Sleep Apnea in Atrial Fibrillation*).

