## **METHODS**

### ***Participant Eligibility Criteria and Process for Recruitment***

We plan to recruit 50 patients with QT prolongation as identified by ICD 10 426.82 from the Cleveland Clinic. At the Cleveland Clinic, we will utilize the Knowledge Program query tool and EResearch along with [name] Registry: Cleveland Clinic internal registry for inherited arrhythmias (IRB: 16-1094) platforms to identify potential recruits. Those patients with congenital LQTS or QT prolongation related to acquired heart disease or arrhythmogenic drugs will be eligible. Approximately ~500 patients/year (42/month) with QT prolongation are evaluated at the Cleveland Clinic. Assuming 50% meet eligibility criteria and 50% of those are interested then ~n=125 patients will be recruited/year (n=16/month over 8 months). This translates into n~150 potential participants over the 8-month recruitment period which exceeds the n=50 cases required to meet sample size requirements.

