## **PROTOCOL**

Potential participants will come to the Cleveland Clinic Clinical Research Unit (CRU) for informed consent, eligible participants will undergo a 12 lead electrocardiogram. If the participants is found to have long QT syndrome ( $QT_c \geq 450$  in men and  $\geq 470$  in women) they will continue on in the study. If they are found to not have long QT syndrome they will exit the study. If continuing on in the study the participant will undergo a fasting venipuncture and blood pressure measurements. The participant will then be shown how to use the portable sleep study hook-up and continuous 12-lead ECG monitoring to be monitored in the home setting. The sleep study and ECG monitors will be returned by a courier service the next morning.

Those participants who are identified to have OSA (apnea hypopnea index  $\geq 5$ , estimate 50% of those recruited) on the portable sleep monitoring will be invited to wear CPAP for 2-3 months with a follow up visit with repeat portable polysomnographic and continuous electrophysiologic assessments and CRU visit for bloodwork and blood pressure.

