**Aim 2. Examine the effect of OSA (AHI $\geq$ 5) treatment for 3 months on QT interval duration.**

For this subgroup of OSA (AHI $\geq$ 5, estimated to be 50% of n=50) and we will perform t-tests to compare pre- and post- treatment mean outcome (Primary outcome: QT duration) and also novel quantitated T wave morphologic measures. For either outcome for which a departure in normality is found (based on the Shapiro-Wilk test) but a transformation of the outcome can not be found to adequately address the issue, we will use the Wilcoxon signed rank sum test to detect a difference in the distribution of the pre- and post- responses. This assessment is not intended to be confirmatory, but rather to provide estimates of variability and effect sizes to inform future studies/randomized trials. Linear regression models will then be developed to QT interval duration at the 3-month visit by conditioning on baseline QT interval duration, baseline OSA, and time from baseline to 3-month visit. Additional adjusted models will carefully consider the covariates list above.

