#### **POWER BY AIM.**

**Specific Aim 1.** A sample size of 50 will be able to detect 0.59 standard deviations with 80% power (and 0.62 with 90% power), assuming a 2-sided alpha level of 0.05 which is sufficient for generation of pilot data.

**Specific Aim 2.** Using a two-sample t-test (2-sided 0.05 alpha-level) to test for a difference in mean variation between the SDB (AHI $\geq$ 5) and no SDB groups, a sample size of 50 (25 with OSA and 25 without OSA) will detect mean differences within 0.46 standard deviations with 80% power and 0.53 standard deviations with 90% power.

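### The Aim 2 power statement counts all 25 expected OSA participants, allows nothing for CPAP refusal or dropout, and sizes a different test from the pre/post comparison planned

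*Combined protocol and SAP*

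**What the plan says.** **Power.** POWER BY AIM, Specific Aim 2, is set up as "Using a two-sample t-test (2-sided 0.05 alpha-level) to test for a difference in mean variation" between participants with and without sleep-disordered breathing. It says that "a sample size of 50 (25 with OSA and 25 without OSA) will detect mean differences", namely "within 0.46 standard deviations with 80% power and 0.53 standard deviations with 90% power".

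**Analysis.** Analytic Method by Aim, Aim 2, takes the subgroup with AHI of at least 5, "estimated to be 50% of n=50", and will "perform t-tests to compare pre- and post- treatment mean outcome". The signed rank test is the fallback. The section says that the assessment is not confirmatory and is meant to supply variability and effect-size estimates for later studies.

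**Flow.** In PROTOCOL, consented people have a 12-lead ECG: "If they are found to not have long QT syndrome they will exit the study". Those found to have OSA on home monitoring are then invited to wear CPAP and return. No acceptance rate is given.

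**Retention.** Clinical Trial Experience/Recruitment and Retention reports, for the group's earlier CPAP studies, "expected retention (drop out range: 10-20" (per cent).

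**Target.** Participant Eligibility Criteria and Process for Recruitment plans to recruit 50 and describes the projected pool as one "which exceeds the n=50 cases required to meet sample size requirements". The Timeline gives a goal of 7-8 participants a month over eight months.

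**The concern.** The same 50 serves as the number recruited, the base for the OSA subgroup and the number in the power statement. Between recruitment and a usable pre/post pair, the plan describes two points at which people can be lost: declining CPAP and not returning. Neither enters the Aim 2 calculation, and that calculation is for a comparison of OSA with no OSA, which is not the Aim 2 analysis.

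Aim 2 exists to give an effect size and a variance for planning a later trial, so its precision is its main product. A reader who takes 0.46 or 0.53 SD as that precision would be relying on a figure that describes neither the planned analysis nor the number of people likely to contribute to it.

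**Working it through.** **Inputs.** From POWER BY AIM: 25 per group, two-sided alpha 0.05, 80% and 90% power. From the Aim 2 analysis section: 50% of 50 have OSA. From the retention section: 10-20% dropout. CPAP acceptance is not in the documents.

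**1. The plan's own figure.** For two groups of 25, the detectable difference in SD units is approximately (z for alpha/2 + z for power) × √(2/25).
- 80%: (1.960 + 0.842) × 0.2828 = 0.79; exact noncentral t, 0.81.
- 90%: (1.960 + 1.282) × 0.2828 = 0.92; exact, 0.94.

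The stated 0.46 and 0.53 are not reproduced. With 25 per group, power is about 36% for 0.46 SD and 45% for 0.53 SD. Reaching the stated power needs about 2 × (2.802/0.46)² = 74.2, that is 75 per group (76 by exact t); the 90% pair gives the same.

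Other readings (80%/90% power) do not match either:
- one-sided, 25 against 25: 0.71/0.84
- 50 per group: 0.57/0.65
- 25 pairs: 0.58/0.68
- 50 pairs: 0.40/0.47

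The stated values would fit change scores in 25 against 25 if the pre/post correlation were about 0.84, since 0.81 × √(2 × 0.16) = 0.46. They would fit 25 pairs expressed in raw outcome SDs if it were about 0.69, since 0.584 × √(2 × 0.31) = 0.46. The plan states no correlation, and PROTOCOL describes a repeat recording only for those with OSA.

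**2. Expected pairs from 50.** Pairs = 50 × 0.5 × acceptance × (1 − dropout).
- Full acceptance: 25 × 0.9 = 22.5 and 25 × 0.8 = 20, so 20-22 complete pairs.
- 80% acceptance (assumption): 18 to 16.
- 60% acceptance (assumption): 13.5 to 12.

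**3. Precision of the planned paired comparison.** Detectable change is from the noncentral t; half-width is t(0.975, n−1)/√n. Units are SDs of the within-person change, which are not the units of a between-group difference.

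| Pairs | 80% power | 90% power | 95% CI half-width |
|---|---|---|---|
| 25 | 0.58 | 0.68 | 0.41 |
| 22 | 0.63 | 0.73 | 0.44 |
| 20 | 0.66 | 0.76 | 0.47 |

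Dropout alone enlarges the detectable change by 0.626/0.584 = 1.07 to 0.660/0.584 = 1.13, that is 7-13%. At the assumed 80% acceptance it is 0.70-0.75 SD at 80% power; at 60%, about 0.83-0.89 SD.

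**4. The Timeline target.** 7 × 8 = 56 and 8 × 8 = 64 participants. Half with OSA gives 28-32. After dropout, 28 × 0.8 = 22.4 to 32 × 0.9 = 28.8, so about 22-29 pairs before refusals.

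**The case against.** Several stronger readings are tempting, and the documents do not support them.

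- *Aim 2 is sized on 25 treated participants and that number is not delivered.* The power sentence compares OSA-status groups. No number of pre/post pairs is stated anywhere, so no stated number is missed. What stands is that the 25 with OSA are the only source of pairs, and that the sentence is offered as the power for the CPAP aim.
- *The plan overstates its interval width.* It gives none.
- *The design cannot yield 25 pairs.* The Timeline's 56-64 is close to 50/(1 − d) for 10-20% dropout, which is 56-63, and could offset much of the loss. But the plan does not call it a dropout allowance, it conflicts with the 50 under recruitment, and the analysis and power sections still work from 50.
- *Exits on the entry ECG reduce the 50.* They need not. The recruitment section speaks of cases, and PROTOCOL applies its 50% OSA estimate to people who have already passed the ECG. This is an ambiguity to settle, not a shown loss.
- *The plan adopts 10-20% dropout.* It is past experience. It is, however, the only retention figure given, and it comes from the group's own CPAP studies.

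It is also fair that inclusion requires ability to complete at least two overnight assessments, which bears on return though not on CPAP acceptance. Chance variation in OSA frequency (about 18-32 of 50 at a true 50%) is wider than the loss to dropout. And the assessment is declared non-confirmatory. These points limit the severity; they do not make the stated figure correct.

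**Conclusion.** The point holds, at low severity. The Aim 2 power statement allows for neither refusal nor dropout, addresses a test other than the planned one, and quotes 0.46/0.53 SD where 25 against 25 gives 0.81/0.94 SD. The larger fault is the test and formula: allowing for dropout alone would not repair the statement, and correcting the formula while keeping 25 pairs would still be somewhat favourable.

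The count of 20-22 pairs is an upper range. It assumes 50 participants with usable baseline recordings, 50% OSA, every one of them accepting CPAP, and the 10-20% past dropout carrying over. It also assumes that CPAP is offered to all with OSA, as PROTOCOL says; the CPAP Intervention section speaks of subjects randomized to CPAP, and the two must be reconciled because the number treated depends on it.

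**What to change.** Make this change together with the correction of the Aim 2 test and formula.

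1. Replace the Aim 2 figure with the paired detectable change and CI half-width for the expected number of pairs, taking the 22- and 20-pair rows of the table above. Say that the unit is the SD of the within-person change, or give the assumed pre/post correlation used to convert it.
2. State the assumed CPAP acceptance and dropout, and show a lower range of pairs if some decline.
3. Define the 50 as participants who pass the entry ECG and have a usable baseline recording.
4. Give one enrolment target, reconciling the 50 under recruitment with the 56-64 implied by the Timeline. If the larger target is intended, recompute from about 22-29 pairs before refusals.

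The cost is protocol and SAP wording and a less favourable stated figure. No extra enrolment is required.

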#### **Alternative/Pitfalls**

1. Although we have experience with successful cross-institutional collaboration and recruitment, it is possible that recruitment efforts may not be successful with the approach as outlined via EResearch and the KP query tool. If this is the case, we will plan to pre-screen patients in electrophysiology clinics.
2. We will not have research-grade time-concordant echocardiography to assess as a covariate factor, however, it is anticipated that many of the patients will have clinical ECHO studies for which we will conduct data extraction.
3. Although there will be heterogeneity in the sample in terms of the etiology of QT prolongation, this will be a strength as albeit we will be somewhat limited in power, we will be able to examine subgroup effect sizes.

#### **Timeline**

Please refer to **Figure 7** for the timeline. The first 2-4 weeks will be dedicated to solidifying protocols, establishing database and personnel training. Recruitment will begin month 1 until month 8 (goal recruitment 7-8 participants per month) with collection of in-tandem sleep monitoring and continuous 12-lead ECG monitoring with blood work. In months 9-12 statistical analyses will be conducted with

preparation of abstracts (submitted to Heart Rhythm and American Thoracic Society meetings) as well as manuscripts entitled “*Association of Obstructive Sleep Apnea and Corrected QT interval and Novel T Wave Morphologic Characteristics*” and “*Impact of Continuous Positive Airway Pressure on Corrected QT interval and Novel T Wave Morphologic Characteristics*” and preparation of an R01 application.

### **Future Directions**

The goals of the application are to overcome existing knowledge gaps in understanding the influence of OSA on cardiac electrophysiology, namely QT prolongation, which predisposes to VTA and cardiac death. The pilot data generated will be key in elucidating the impact of OSA on predisposing to cardiac vulnerability in those who are predisposed, i.e. have congenital or acquired QT interval prolongation. Data generated will provide important information on effect size of OSA treatment on QT interval prolongation which will inform future studies.

### **Relevance and Benefit to CTSC/Translational Research**

The insights garnered from the proposed pilot work will be scalable and provide key interventional data to lead to a larger clinical trial. We will also use CRU resources for blood work blood pressure assessments and statistical support. The application has a high likelihood of success given the public health importance of examination sleep-lethal cardiac arrhythmogenicity to identify novel preventative approaches in the context of a cogent biologic basis, limited existing clinical data contributing to a large existing knowledge gap and scientific experience of the investigators, thereby ideally positioning us for this critical translational opportunity to then take to the next level via application for NIH or American Heart Association funding.

### **Data Sharing**

We plan to make available de-identified, non-sensitive, individual-level information on objective sleep characteristics, subjective sleep health and medical history (e.g. comorbid factors and medication use) and sociodemographics (e.g., age, gender education level). We will submit the data generated from the current proposal to the NIH funded National Sleep Research Resource (NSRR). The National Sleep Research Resource (NSRR) offers free web access to large collections of de-identified physiological signals and clinical data elements collected in well-characterized research cohorts and clinical trials. The NSRR is a public resource which provides opportunities for investigators to address critical scientific questions of interest.

